*Smoking: Will include both tobacco and marijuana at baseline, and marijuana only at Weeks 8 and 12. **H&P, laboratory tests, and ECG within previous 90 days is acceptable at screening visit. (At Week 12: The H&P, thyroid test, and ECG do not need to be repeated.) If baseline level was between 3x-5x ULN, ALT and AST needs to be repeated at week 4 and week 8 visit. At Week 8, GGT needs to be repeated. ^aVital signs and breathalyzer on Week 2, 6, 10 may be omitted due to COVID-19 reduction of in-person visits. ^bPsychophysiological assessments are optional so as to not be a barrier to enrollment or randomization. ***Day of Randomization is on Baseline. The schedule of follow-up visits is anchored to Baseline. ****CAPS-5 and C-SSRS can be administered prior to day of baseline so long as it is within one week of day of randomization and scores are entered as baseline. ****C-SSRS can be done either at screening or baseline visit, as well as Week 8. ^{\$}Baseline and week 8 drug dispensing will occur on day 1 if not participating in psychophysiology testing and on day 2 if participating in testing

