7.3.3 BASELINE AND RANDOMIZATION VISITS

The investigators and CRCs provide ongoing support and education during the study to reinforce the participants' commitment and resolve logistical barriers to keeping the appointments. Participant burden is kept to a minimum (i.e., small number of assessments and low frequency). Adherence and attendance are vital to the success of both treatment and the study. Patient education on study procedures and the treatment approach in the study is the cornerstone to promote adherence. To maximize participant retention, study coordinators are trained to have a substantial focus, especially in the first several meetings with participants, on developing a strong alliance, educating them about the study, understanding the importance of adhering to treatment, what is expected of them as a study participant, and eliciting commitment.

At the baseline visit, the research team evaluates the participant per the study instruments listed in the Schedule of Assessments table in 7.3.1. Participants undergoing the optional two-day psychophysiological assessments, as described above, will complete both days of the psychophysiological testing prior to beginning the study medication.

The research medication provider enters the medication orders (one for XR-NTX and one for SL-BUP) and the local site pharmacy dispenses the study medication according to the randomized assignment to one of two treatments:

- **Treatment A (SL-BUP 2mg + XR-NTX 380mg) or**
- **Treatment B (SL-PLC and XR-PLC).**

SL-BUP is taken daily and XR-NTX is given every 4 weeks. All medications are dispensed by local site pharmacies with clearly labeled instructions.

The participant receives the first dose of XR-NTX injectable in the research clinic and remains in the clinic under the supervision of the research team for approximately 1 hour after the 1st dose is administered.

The medication provider or trained CRC reviews the medication instructions with the participant (how to administer sublingual, keeping up with medication dosing, and need to return any

unused medication to the research medication provider at the next visit). The participant initiates SL-BUP on the following day.

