		
The TLFB assessment is given at screening, baseline, and weeks 1, 2, 4, 6, 8, 10, and 12. The screening measurement uses a 90-day recall period whereas the subsequent (post treatment follow up) measurements use a recall period of “since the last measurement.” The baseline WHO risk level will be derived from TLFB data collected at both the screening and baseline visit. The look-back period to define the WHO risk level will be conducted over 28 consecutive days and based on the average number of reported standard drinks during those 28 consecutive days. Each derived outcome measure for a specific timepoint will be based on the baseline visit date. In the event 28 consecutive days are not captured for the full look-back period, participant data will be excluded from analyses in the event the number of total days included in look-back period is less than one standard deviation of the entire population.

Percent Heavy Drinking Days (%HDD)	Continuous (range between 0 and 100)	
Percent Heavy Drinking Days (%HDD) is measured via the Timeline Follow Back instrument (Sobell et al., 1996). The screening (baseline) measurement uses a 90-day recall period whereas the subsequent (post treatment follow up) measurements use a recall period of “since the last measurement.” Baseline %HDD will be derived from TLFB data collected at both the screening and baseline visit. The look-back period to define %HDD will be conducted over 28 consecutive days and based on the number of heavy drinking days reported during this time period. Each derived outcome measure for a specific timepoint will be based on the baseline visit date. In the event 28 consecutive days are not captured for the full look-back period, participant data will be excluded from analyses in the event the number of total days included in look-back period is less than one standard deviation of the entire population.
 
A heavy drinking day is defined as follows:
 
>4 standard drinks/sessions for men and >3 standard drinks/sessions for women

Variable	Type	Definition
CAPS-5 Total Symptom Severity Score	Continuous (range between 0 and 80)	CAPS-5 total symptom severity score is measured via the Clinician-Administered PTSD Scale For DSM-5 (CAPS-5). The score is calculated by summing severity scores for the 20 DSM-5 PTSD symptoms (Weathers et al., 2013), with a higher score indicating worse PTSD symptoms.
Exploratory Outcomes		

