As mentioned above, %HDD is assessed by the TLFB and is collected at baseline and weeks 2, 4, 6, 8, 10, and 12. The treatment effect on the clinical criteria of AUD as measured by %HDD over time will be assessed using a generalized-linear mixed model to account for temporal correlation between measurements and the clustering of the data. A similar model to that listed in Section 9.3.1 will be run to produce adjusted marginal means to report and test for differences in mean %HDD for the placebo and BUP/NTRX groups, providing 95% confidence intervals and a p-value for the difference between them. NOTE: the lookback period to derive %HDD will be performed at 28-days, each derived measure at a specific timepoint based on the baseline visit date. Sensitivity analysis maybe also performed using a 14-day look-back period.

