Appendix B List of Potential Tables and Figures

Tables
a) Demographics and Baseline Characteristics by Treatment Group
b) Comparison of Primary Composite Outcome Measure by Treatment Group
c) Comparison of Change in %HDD by Treatment Group
d) Comparison of Change in CAPS-5 by Treatment Group
e) Comparison of Change in PCL-5 by Treatment Group
f) Comparison of Change in PHQ-9 by Treatment Group
g) Comparison of Change in VR-12 Measures by Treatment Group
h) Comparison of AEs by Treatment Group
Figures
a) Study CONSORT
b) Line plots with error bars for mean change from baseline by treatment group for the following outcome measures: CAPS-5, %HDD, PCL-5, PHQ-9, and VR-12
c) Box and whisker plots for vital measures
d) Bar charts for missed SL-BUP and NTX injections by treatment group

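### The 28-day look-back makes Week 2 %HDD half pre-randomisation drinking and overlaps neighbouring two-weekly values; the Week 8 contrast is not affected

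*SAP*

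**What the plan says.** SAP 9.2 lists %HDD among the primary outcomes and defines it this way: "The look-back period to define %HDD will be conducted over 28 consecutive days and based on the number of heavy drinking days reported". It takes baseline %HDD from the Timeline Follow-Back (TLFB) interviews at screening and baseline. On recall it says: "The screening (baseline) measurement uses a 90-day recall period". Later interviews cover the time since the previous one.

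SAP 9.3.2 says %HDD is "collected at baseline and weeks 2, 4, 6, 8, 10, and 12" and sets the window: "the lookback period to derive %HDD will be performed at 28-days, each derived measure at a specific timepoint based on the baseline visit date". It analyses these values with a model similar to the CAPS-5 model in 9.3.1, whose code requests adjusted means for every treatment-by-visit cell. A 14-day look-back is mentioned only as a sensitivity analysis that may be done.

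SAP Appendix B includes this among the possible figures: "Line plots with error bars for mean change from baseline by treatment group for the following outcome measures: CAPS-5, %HDD", followed by other scales.

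On timing, Protocol 7.3.1 says: "Day of Randomization is on Baseline. The schedule of follow-up visits is anchored to Baseline". Protocol 7.3.3 gives the first injection in the clinic and adds: "The participant initiates SL-BUP on the following day".

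No section ends a look-back window at randomisation or removes Week 2 from the %HDD analysis.

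**The concern.** A 28-day window is twice the gap between the visits at which it is applied. The first post-baseline window therefore reaches back before randomisation, and each later one reaches into the window before it.

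Two outputs are at stake. One is the Week 2 treatment contrast, which the model will produce and which will naturally be read as an effect of two weeks of treatment. The other is the line plot of change over time, where neighbouring points are partly the same data.

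The SAP also leaves room for two derivations at Week 2. An analyst who follows the 28-day rule uses 14 days from before randomisation. An analyst who starts at day 1 has only 14 of the 28 days. The SAP should settle this before unmasking.

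**Working it through.** **Inputs.** Window length 28 days, with timepoints counted from the baseline date (SAP 9.2 and 9.3.2). Visits at baseline and Weeks 2 to 12, every 14 days (SAP 9.3.2). Baseline is the day of randomisation, taken as day 0 (Protocol 7.3.1). Daily sublingual drug starts on day 1 (Protocol 7.3.3). The plan gives no window table to reproduce, so the windows are built from its rule.

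**Step 1: windows.** The window for week w is days 7w - 27 to 7w.

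| Visit | 28-day window | Days on or before day 0 | Days shared with next visit |
|---|---|---|---|
| Baseline | -27 to 0 | 28 | 14 |
| Week 2 | -13 to 14 | 14 | 14 |
| Week 4 | 1 to 28 | 0 | 14 |
| Week 6 | 15 to 42 | 0 | 14 |
| Week 8 | 29 to 56 | 0 | 14 |
| Week 10 | 43 to 70 | 0 | 14 |
| Week 12 | 57 to 84 | 0 | none follows |

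Week 2 has 14/28 = 50% of its days before treatment. If day 0 were counted as a treated day because of the injection, this would be 13/28 = 46%. Windows four weeks apart share no days.

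**Step 2: can the Week 2 window be filled?** Yes. The 90-day screening recall and the baseline interview cover days -13 to 0. The SAP 9.2 rule for windows with too few captured days would therefore not normally exclude it.

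**Step 3: size at Week 2.** Randomisation makes the expected pre-baseline difference between arms zero. The expected Week 2 contrast is then (14 x 0 + 14 x D)/28 = D/2, where D is the mean effect over days 1-14. If the effect is constant from day 1, D is the full effect and Week 2 shows half of it.

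**Step 4: shape of the curve.** Each 28-day value is the average of two consecutive 14-day values: H28(w) = [H14(w-2) + H14(w)]/2. If the 14-day contrasts at baseline, Week 2 and Week 4 were 0, D, D, the 28-day contrasts would be 0, D/2, D. A single step is drawn as a two-step ramp.

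**Step 5: actual visit dates instead.** With the ±7-day visit window, a look-back ending on the actual Week 2 visit (day 7 to day 21) would be 75% to 25% pre-randomisation. Anchoring to the baseline date fixes the share at the nominal 50%.

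**Step 6: alternatives.** A 14-day look-back gives days 1-14, 15-28, 29-42, 43-56, 57-70 and 71-84. A 28-day look-back at Weeks 4, 8 and 12 only gives days 1-28, 29-56 and 57-84. Both have 0% pre-randomisation days and 0% overlap between successive post-baseline values.

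**The case against.** The strongest reply is that no planned formal test depends on Week 2. SAP 7.7 plans one, the composite at Week 8. Protocol 10.4.2 makes Week 8 the effect of interest for the components too. No document states a Week 2 hypothesis for %HDD, and Appendix B lists only potential figures. A trailing 28-day measure is also a legitimate smoothed quantity if labelled as such, and it matches the look-back used for the composite. All of this stands and limits the point. It does not remove it: the Week 2 contrast will still be produced, for an outcome that SAP 3.1.2 sets as a primary objective over the 8-week period, and nothing would tell a reader that half of the value precedes treatment.

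A reader might infer more than the documents support:

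- **That the Week 8 result is biased.** Its window contains no pre-randomisation day and shares none with baseline, Week 4 or Week 12. The composite is modelled only at Weeks 4, 8 and 12, whose windows do not overlap.
- **That the 8-week %HDD effect is understated.** An equal-weight average over Weeks 2, 4, 6 and 8 would give (0.5 + 1 + 1 + 1)/4 = 87.5% of an effect constant from day 1, but no section plans such an average.
- **That overlap with a compound-symmetry model spoils the standard errors.** Overlap does make correlation unequal across lags. However, a simulation (400 trials of 45 per arm, 30% dropout) gave Week 8 empirical SD and model SE of 6.08 and 6.04 with all six visits, against 6.16 and 6.36 with Weeks 4, 8 and 12 only. Rejection under no effect was 5.3% and 5.0%, with a Monte Carlo error of about 1.1 points. Its drinking rates and variances are assumptions, not document figures, but it shows no material harm. SAP 9.3.2 also asks only for a similar model.
- **That people leaving between Weeks 2 and 4 contribute only a half-pre-treatment value.** They also have a baseline value. Protocol 5.4.2 and 7.3.6 call for exit procedures that include the TLFB, so later drinking can be captured.
- **That early benefit will be misreported as gradual.** This presumes immediate onset, which no document establishes.

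It can also be said that SAP 9.2 foresees look-backs with fewer than 28 days. That rule concerns days not captured, so it does not clearly permit cutting the Week 2 window at baseline.

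**Conclusion.** The point holds with limited reach. As written, Week 2 %HDD is 14/28 pre-randomisation drinking that is also in the baseline value, and its expected treatment contrast is half the mean effect over days 1-14. From Week 2 to Week 10, each value shares half its days with the next, so the two-weekly curve is a moving average that spreads any change over two points. The Week 8 %HDD contrast and the composite are not affected.

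The window arithmetic is exact on the nominal schedule. It assumes that timepoints are counted from the baseline date, as the SAP says, and that the window is not silently cut at baseline. Showing half the full effect at Week 2 further assumes an effect constant from day 1.

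**What to change.** In SAP 9.3.2:

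1. State that no post-baseline %HDD window may include days on or before the baseline visit.
2. Report 28-day %HDD at Weeks 4, 8 and 12 (days 1-28, 29-56 and 57-84), the visits at which the composite is modelled.
3. Make the 14-day look-back (days 1-14, 15-28, and so on to 71-84) the definite derivation for any Week 2 to Week 12 curve, and label the Appendix B figure with the window used.

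No new data are needed. There are two small costs. Participants whose only post-baseline drinking data end before Week 4 would contribute to the 14-day series but not to the 28-day model. The 14-day values are also somewhat noisier, because each rests on half as many days. The change should be made before unmasking, so that the window is not chosen with results in view.

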9.4 Exploratory Efficacy Analysis Methods

9.4.1 PCL-5

While the CAPS-5 is considered the gold standard for diagnosing PTSD, the PCL-5 is often used to screen for PTSD and monitor symptom changes before, during, and after treatment. A total symptom severity score ranges from 0 to 80 (Weathers et al., 2013). The PCL-5 is collected at baseline and weeks 1, 2, 4, 6, 8, 10, and 12. The treatment effect on PTSD as measured by the PCL-5 over time will be assessed using a generalized-linear mixed model

to account for temporal correlation between measurements and the clustering of the data. A similar model to that listed in Section 9.3.1 will be run to produce adjusted marginal means to report and test for differences in mean PCL-5 for the placebo and BUP/NTRX group, providing 95% confidence intervals and a p-value for the difference between them.

9.4.2 PHQ-9

The PHQ-9 is the major depressive disorder (MDD) module of the full PHQ. This instrument is used to provisionally screen, diagnose, and monitor depression and grade severity of symptoms in general medical and mental health settings (Kroenke K., Spitzer R., Williams, J., 2001). A total symptom severity score ranges from 0 to 27. The PHQ-9 is collected at baseline and weeks 4, 8, and 12. The treatment effect on depression as measured by the PHQ-9 over time will be assessed using a generalized-linear mixed model to account for temporal correlation between measurements and the clustering of the data. A similar model to that listed in Section 9.3.1 will be run to produce adjusted marginal means to report and test for differences in mean PHQ-9 for the placebo and BUP/NTRX group, providing 95% confidence intervals and a p-value for the difference between them.

9.4.3 VR-12

The VR-12 is a patient-reported global health measure that is used to assess a patient's overall perspective of their health (Jones, Kazis, Lee, et al., 2001). Answers on the 12-item questionnaire are summarized into two scores, a physical component score (PCS) and a mental component score (MCS). The PCS and MCS scores are derived using an algorithm that is referenced to a metric centered at 50.0 (with a standard deviation of 10) using the 2000–2002 US Medical Expenditure Panel Survey population. The VR-12 is collected at baseline and weeks 8 and 12. The treatment effect on these global health measures over time will be assessed using a generalized-linear mixed model to account for temporal correlation between measurements and the clustering of the data. A similar model to that listed in Section 9.3.1 will be run to produce adjusted marginal means to report and test for differences in mean PCS and MCS for the placebo and BUP/NTRX group, providing 95% confidence intervals and a p-value for the difference between them.

9.4.4 Phosphatidyl Ethanol (PEth)

Testing for phosphatidyl ethanol (PEth) is a relatively new tool for detecting and grossly quantifying a person's chronic alcohol consumption. PEth values were collected at baseline and weeks 8 and 12. At each collection timepoint, results were reported as either "positive" or "negative", and if "positive", the PEth value in the blood was reported in ng/mL. For analysis purposes, "negative" results will have a PEth value inputted as 5 ng/mL, the midpoint of the 'not detectable range' (which is reported as less than 10 ng/mL). The treatment effect on PEth measurement over time will be assessed using a generalized-linear mixed model to account for temporal correlation between measurements and the clustering of the data. A similar model to that listed in Section 9.3.1 will be run to produce adjusted marginal means to report and test for differences in mean PEth for the placebo and BUP/NTRX group, providing 95% confidence intervals and a p-value for the difference between them.

9.5 Safety Analysis Methods

9.5.1 Adverse Events

Any AEs will be listed and summarized by system organ class and preferred event term. Summaries will include the number of individuals experiencing events over the duration of the study. These summaries will be created for all AEs and AEs by severity (mild or moderate vs. severe or greater). Summaries will be provided by treatment group. If models can be run, point and confidence interval estimates of the risk difference will be obtained by modeling the probability of experiencing at least one adverse event. The model is specified with the equation:

$$g(E(Y_{ij})) = \beta_0 + \beta_1 \text{Treatment}_{ij} + s_i + \varepsilon_{ij}$$

Where $g(E(\cdot))$ indicates the identity link function on the expected value of Y , Y_{ij} is the occurrence of an AE outcome (any AE, any SAE, and any related AE) in subject i , β_0 is the intercept, β_1 is the treatment group coefficients, s_i is a random subject effect, and ε_{ij} is the residual error term.

Point and confidence intervals for the difference in experienced AE proportion between treatment groups will be estimated with a generalized linear mixed model (GLMM), assuming a binomial distribution and identity link. GLMMs are a flexible generalization of the linear mixed effect model that allows response outcomes to have an error distribution other than the normal distribution (McCullagh, & Nelder, 1989). Statistical analysis modeling will be carried out utilizing SAS/STAT PROC GLIMMIX (SAS Institute Inc. 2017) with the general structure of the SAS code for this model is listed below:

```
proc glimmix data=anlyaedata;
  class patient treatment;
  model any_ae = treatment / link=identity dist=binomial;
  random int / subject=patient;
run;
```

A similar model will be run for the difference in proportion of withdrawn subjects due to adverse events between treatment groups. If the above specified models cannot be fit due to limitations of the study data, frequencies will be analyzed using chi-square test.

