4 STUDY DESIGN AND ENDPOINTS

4.1 DESCRIPTION OF THE STUDY DESIGN

This randomized, double-mask, placebo-controlled, multi-site study evaluates the efficacy of SL-BUP combined with XR-NTX in the treatment of comorbid AUD and PTSD. In addition to the primary clinical outcomes for AUD and PTSD, pre- and post-treatment psychophysiological correlates of fear and alcohol craving include 1) measures of the extinction of fear-potentiated startle and 2) measures of psychophysiological reactivity to trauma stimuli and alcohol cues.

Recruitment is based on convenience sampling of treatment-seeking veterans, nonveterans, and active duty service members. Upon contact with a potential participant, the study team member describes the study and reviews initial eligibility criteria (prescreening under an approved HIPAA waiver). Persons meeting initial criteria are given a consent form to read and discuss with research team members, family and/or providers. Persons who provide written informed consent are scheduled for an initial screening and baseline visit.

Following screening and baseline visits, eligible patients are randomized to receive one of two treatments in a double-mask fashion for 12 weeks.

- **Treatment A (SL-BUP 2mg and XR-NTX 380mg) or**
- **Treatment B (SL-PLC and XR-PLC).**

The treatment allocation ratio for the treatment vs. placebo (PLC) regimens is **1:1** and is stratified by site, presence of concomitant antidepressants, and gender using a random permuted block scheme with variable block size.

The optional psychophysiological studies are conducted at baseline (2-day testing), Week 2 (1-day testing), and Week 8 (2-day testing). The participants are assessed for outcomes on Weeks 1, 2, 4, 6, 8, 10, and 12. Primary and secondary efficacy endpoints are at Week 8. At Week 8, participants remain on the assigned drug or placebo for an additional 4 weeks to allow for a 12-week endpoint. Study medication is discontinued at Week 12 and participants return at Week 14 for evaluation of withdrawal side effects.

All Adverse Events occurring during the clinical trial are collected at each visit, documented, and reported by the PI according to the specific procedures detailed in Section 8.

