8.1.1 DEFINITION OF ADVERSE EVENTS (AE)

An Adverse Event (AE) is any untoward medical occurrence temporally related with the use of a drug in humans, whether or not considered drug related per 21 CFR Part 312.32(a). An adverse event (also referred to as an adverse experience) can be unfavorable and unintended sign (e.g., an abnormal laboratory finding), symptom, or disease temporarily associated with the use of a drug and does not imply any judgment about causality. An AE can arise with any use of the drug (e.g., off-label use, use in combination with another drug) and with any route or administration, formulation, or dose, including an overdose. For purposes of this study, a laboratory abnormality (i.e., out of the normal range) that is considered not clinically significant is not considered an AE.

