10.4.4 SAFETY ANALYSES

The safety analyses population includes all randomized participants. These analyses will include those participants who have reported an adverse event as well as those who do not report an adverse event. The incidence of treatment emergent adverse events, type of adverse events, and frequency of withdrawals due to an adverse event will be summarized by treatment group. Appropriate statistical comparisons will be made between treatment groups in terms of 1) rates of adverse events, 2) discontinuation due to adverse events, and 3) side effect scales. Rates will be compared using time to event hazard analysis. Frequencies will be analyzed using the chi square or Fisher Exact test. The scales will be examined using non-parametric analyses when appropriate. This study is not powered as an equivalence study so the non-significance of differences between groups does not truly imply equivalence.

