3.2.3 Safety Outcomes

Rates, severity and relatedness of adverse events including serious adverse events, study drug-related adverse events, and deaths will be evaluated. See section 8 of the protocol for specific details on safety parameters (i.e. definitions of AEs) and classifications (i.e. severity, relationship, and expectedness definitions).

[figure not shown]

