Phosphatidyl ethanol (PEth)	Continuous (range between 0 and >210 ng/mL)	
Phosphatidyl ethanol (PEth) are a series of abnormal phospholipids located in the cell membrane and formed in the presence of ethanol and phospholipase D. PEth serves as a biomarker of alcohol ingestion in the past 2-3 weeks using liquid chromatography tandem mass spectrometric assessment of human blood (whole or dried spots). PEth in blood is often used as a marker of chronic alcohol use and was collected at baseline and weeks 8 and 12.
 
At the present time, the international scientific community has not yet established a cut-off value for PEth concentration in blood to be used for differentiating an acceptable social ethanol intake (<40 g for males and <20 g for females, according to the WHO parameters), from an at-risk-alcohol-use (40–60 g/die) and chronic excessive drinking behavior (>60 g/die). However, per LabCorp, PEth levels in excess of 20 ng/mL are considered evidence of moderate to heavy ethanol consumption.

Safety Outcomes		
Adverse Events	Counts and proportions	Total number and proportion of treatment emergent adverse events. Comparison of AE rates by treatment group will also be stratified by type and severity.
Withdrawals due to Adverse Events	Proportion	Proportions of individuals by treatment group who withdrew from the study due to adverse events
Adherence and Retention Outcomes		

Variable	Type	Definition
Serum Buprenorphine and Norbuprenorphine	Continuous	
Buprenorphine and its metabolite norbuprenorphine are assayed using liquid chromatography tandem mass spectrometry by a commercial laboratory. Sample results are available via the commercial laboratory portal using a study specific username/password combination and the unique participant code/requisition number.
 
To assess medication adherence, blood samples collected at study weeks 8 and 12 will be tested for buprenorphine and its metabolite, norbuprenorphine, using quantitative assessments.

Pill Count	Count and proportion	
A dosing log case report form (CRF) is completed weekly (or since the last in-person visit) for each participant. The number of completed NTX injections received (at baseline, week 4, and week 8) is recorded, as well as the number of missed SL-BUP pills per week. For each medication (NTX and SL-BUP), the proportion of subjects who missed any treatment will be derived, as well as the total number of missed injections or pills, per participant.

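### SAP safety analyses omit the side-effect-scale comparison in Protocol 10.4.4, leaving COWS and C-SSRS with no by-arm summary; neither document plans one for liver enzymes

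*SAP*

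**What the plan says.** **Protocol.** Section 10.4.4 lists the between-arm safety comparisons as "1) rates of adverse events, 2) discontinuation due to adverse events, and 3) side effect scales". It gives the third a method: "The scales will be examined using non-parametric analyses when appropriate". It names no instrument.

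The schedule in 7.3.1 places COWS at screening, Week 12 and Week 14, and C-SSRS at screening or baseline and at Week 8. Section 4.1 gives the purpose of the last visit: "participants return at Week 14 for evaluation of withdrawal side effects". The instrument table in 7.1.1 says C-SSRS tracks emergent suicidality at Week 8. Under 7.2.1, ALT and AST are measured at screening and at Week 12 or early termination. They are rechecked at Weeks 4 and 8 only when the baseline value was 3x to 5x ULN. GGT is taken at baseline, Week 8 and Week 12. Section 8.1.1 adds that "a laboratory abnormality (i.e., out of the normal range) that is considered not clinically significant is not considered an AE".

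**SAP.** Section 3.2.3 defines the safety outcomes: "Rates, severity and relatedness of adverse events including serious adverse events, study drug-related adverse events, and deaths will be evaluated". Section 9.2 lists two safety variables, adverse events and "Proportions of individuals by treatment group who withdrew from the study due to adverse events". Section 9.5 has one subsection, 9.5.1 Adverse Events, which opens: "Any AEs will be listed and summarized by system organ class and preferred event term". Appendix B lists one safety table, AEs by treatment group, and one other safety display: "Box and whisker plots for vital measures". The DSMB report in Appendix A has no scale or laboratory summary.

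**The concern.** Protocol 10.1 has the SAP guide the analysis. If the SAP is followed as written, one of the three safety comparisons in the protocol is not made, and the SAP does not say why.

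The measures affected bear on risks that Protocol 2.3.1 discusses: dependence and withdrawal with buprenorphine, suicide-related events with extended-release naltrexone, and hepatitis with buprenorphine. The same section expects withdrawal to be highly unlikely at this dose with naltrexone on board. COWS at Weeks 12 and 14 is the measurement that could show whether the arms differ on that point, yet no by-arm display of it is planned.

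Specifying these displays before unmasking also prevents safety tables from being chosen after the results are known.

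**Working it through.** This is mainly a comparison of texts.

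| Protocol 10.4.4 comparison | SAP counterpart |
|---|---|
| AE rates | 3.2.3, 9.2, 9.5.1, Appendix B |
| Discontinuation due to AEs | 9.2, 9.5.1 |
| Side effect scales | None |

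**Where the measures appear in the SAP.** COWS and C-SSRS appear only in the abbreviations, protocol history, eligibility criteria and assessment schedule. Liver enzymes appear only in the protocol history and eligibility criteria, and within the Labs/ECG row of the schedule. None has an outcome definition, method, table or figure.

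**How far the AE tables stand in for liver values.** Four protocol rules act together:
- Entry is allowed up to 5x ULN (5.2).
- Raised enzymes are expected from drinking (note to 5.2).
- A condition present at screening counts as an AE only if it deteriorates (8.3).
- An abnormality judged not clinically significant is not an AE (8.1.1).

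A moderate shift in enzymes in one arm could therefore stay out of the AE tables.

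**How far AE counts inform on suicidality.** Protocol 2.3.1 gives 0.3% for suicide-related events leading to discontinuation of extended-release naltrexone. Assume that this rate applies here. The chance of at least one event in the active arm is 1 − (1 − 0.003)^n:
- n = 45: 1 − 0.997^45 = 12.6%
- n = 45 × 0.70 = 31.5, after the 30% attrition in Protocol 10.5: 9.0%

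Event counts alone would say little about a difference between arms.

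**What the added tables could show.** Neither document gives expected rates for a raised COWS score, so the rates below are assumptions. Exact two-sided Fisher power at alpha 0.05:

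| Active v placebo | 45 per arm | 32 per arm |
|---|---|---|
| 20% v 2% | 0.734 | 0.458 |
| 25% v 5% | 0.708 | 0.484 |
| 15% v 2% | 0.450 | 0.218 |

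The 32 is 31.5 rounded up. The approximate 95% half-width for a difference is 1.96 × √[p₁(1−p₁)/n + p₂(1−p₂)/n]. With 10% in each arm:
- n = 45: 1.96 × √(0.18/45) = 0.124
- n = 32: 1.96 × √(0.18/32) = 0.147

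On complete data a large difference would probably be detected. After the expected attrition, none of these cases reaches even 50% power. An estimate with its interval is the more useful summary.

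**The case against.** **The protocol names no scale.** This stands. The instrument table gives the COWS purpose as checking baseline eligibility, and no instrument is called a side-effect scale. The link rests on inference: COWS is repeated at Weeks 12 and 14, and Week 14 exists to look for withdrawal. C-SSRS is inferred in the same way from its stated tracking purpose. CIWA-Ar is a weaker candidate. It measures alcohol withdrawal, and Protocol 7.3.2 repeats it to confirm stability for referral.

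**The SAP dropped nothing on laboratory values.** This also stands. A reader might infer that a liver-enzyme comparison was planned and then removed, but 10.4.4 never listed one. That gap is in both documents.

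**The AE route covers these hazards.** This stands in part. AEs are collected through Week 14, a nurse calls three to five days after medication stops, out-of-range laboratory values are reviewed, and ALT/AST grading starts at 1.1x ULN. SAP 9.5.1 summarises what is recorded by arm, term and severity. PHQ-9, which has one suicidality item, is compared by arm, though only as a total score. A reader might infer that the trial would report nothing on withdrawal, suicidality or liver injury by arm. The documents do not support that.

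**The comparison is not forbidden.** True. Protocol 10.4.4 remains in force, and Appendix B is headed as a list of potential outputs. The comparison is left unspecified, with no instrument, time point or summary measure fixed in advance.

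**Conclusion.** The point holds in a limited form. One of three between-arm safety comparisons in Protocol 10.4.4 has no counterpart in the SAP, and no reason is given. On the reasonable but inferred reading that COWS and C-SSRS are the scales meant, scores from two instruments at three instrument-visits (COWS at Weeks 12 and 14, C-SSRS at Week 8) have no planned by-arm summary. Liver enzymes have none in either document, and the AE definition filters what would otherwise reach the AE tables.

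The gap concerns measured scores and values, since recorded events are still compared. The textual finding depends on no sample-size figure. The power figures rest on assumed rates and show only that formal tests would often be inconclusive at this size. The SAP should be amended, at little cost. The omission does not undermine the planned AE analysis.

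**What to change.** Add the following to SAP 9.2, 9.5 and Appendix B. Show each by arm, with the number assessed and the between-arm estimate with its 95% interval:
- COWS score at Week 12 and at Week 14.
- Number and proportion with new C-SSRS ideation or behaviour at Week 8.
- Baseline-to-Week 12 shift tables in ULN categories for ALT, AST and GGT, whether or not the value was judged clinically significant, with GGT also at Week 8. Show Week 4 and Week 8 ALT/AST separately, for participants with a baseline value of 3x to 5x ULN only. Others are not routinely sampled then, so pooling would mix uneven sampling.

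State in the SAP which instruments are the side effect scales of Protocol 10.4.4. If any comparison planned there is not carried over, record that and the reason. Do this before unmasking.

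The cost is a few extra tables from assessments already scheduled, with no new visit or measurement. The intervals will be wide, and the SAP should say that a lack of difference is not evidence of equivalence, as Protocol 10.4.4 already does for its safety comparisons.
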